6. RESPONSE MEASURES

6.1. SAFETY

The safety endpoint is defined as the incidence of Major Adverse Events (MAE), defined as the composite of the following as determined by the independent Clinical Events Committee (CEC). Event definitions are provided in §8.7.7.

- *All-Cause Death;*
- *Bowel Ischemia;*
- *Myocardial Infarction;*
- *Paraplegia;*
- *Renal Failure;*
- *Respiratory Failure;*
- *Stroke;*
- *Procedural Blood Loss $\geq 1000cc$.*

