6.3. ADDITIONAL EVALUATIONS

Additional evaluations include:[†]

- **Procedural and In-Hospital Evaluations:**
 - Volume of contrast media used
 - Fluoroscopy time
 - Total procedure time[‡]
 - Time in ICU[§]
 - Estimated blood loss
 - % requiring blood transfusion
 - Anesthesia time[¥]
 - Time to hospital discharge[£]
- **Mortality**, all-cause and aneurysm-related, within 30 days, at six months, and annually at 1 through 5 years.
- **MAE Individual Components** within 30 days, at six months, and annually at 1 through 5 years.
- **Composite MAEs** after 30 days, at six months, and annually at 1 through 5 years.
- **Aneurysm Rupture** within 30 days, at six months, and annually at 1 through 5 years.
- **Conversion to Open Repair** within 30 days, at six months, and annually at 1 through 5 years.
- **Adverse Events** (serious and non-serious) within 30 days, at six months, and annually at 1 through 5 years.
- **Distal Blood Flow** pre-discharge and at 30 days, six months, and annually at 1 through 5 years as determined by ankle-brachial index measurements and changes over time.
- **Endograft Performance** at 30 days, six months, and annually at 1 through 5 years as assessed by aneurysm sac diameter change from the first post-operative visit; device migration; and incidence of endoleak.
- **Renal Function** pre-discharge and at 30 days, six months, and annually at 1 through 5 years, as assessed by the estimated glomerular filtration rate (eGFR) and changes over time.
- **Renal Stent Graft Patency and Integrity** within 30 days, at six months, and annually at 1 through 5 years, as determined by contrast-enhanced CT scan, and as assessed by the independent core laboratory, inclusive of:
 - Patent luminal flow
 - Absence of kinking, stenosis, or occlusion (>60%)
 - Absence of stent fracture
 - Absence of graft failure
 - Absence of renal infarct >30%

[†]Event definitions are provided in §8.7.7.

[‡]Elapsed time from the first break of skin to final closure (i.e., skin to skin time).

[¥]Elapsed time from the initiation to the end of the anesthesia protocol.

[§]Elapsed time from the first administration of anesthesia to release from the ICU or post-anesthesia care unit providing ICU-level care. If the patient is not admitted to the ICU, this is defined as 0 hours.

[£]Elapsed time from initiation of the procedure to physical discharge from the hospital.

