8.7.4. Anticipated Adverse Events

Adverse events that could potentially occur during this investigation are called anticipated adverse events and are listed in alphabetical order:

- Access site complications and sequelae (e.g., dehiscence, infection, pain, hematoma, pseudoaneurysm)
- Allergic reaction to contrast agent (e.g., pruritus, urticaria, bronchospasm, angioedema, hypotension or anaphylaxis that occurs during or post-procedure)
- Amputation
- Anesthetic complications and sequelae (e.g., aspiration)
- Aneurysm enlargement
- Aneurysm rupture
- Arterial damage or trauma (e.g., bleeding, perforation, dissection, rupture)
- Arterial or venous thrombosis and/or pseudoaneurysm
- Arteriovenous fistula
- Bleeding requiring transfusion and/or surgical intervention
- Bowel complications (e.g., ileus, ischemia, infarction, necrosis)
- Cardiac complications and sequelae (e.g., arrhythmia, myocardial infarction, congestive heart failure, hypotension, hypertension)
- Catheter fragmentation and sequelae (e.g., embolization, vessel trauma)
- Claudication
- Coagulopathy
- Death (due to any cause)
- Edema
- Embolization (micro and macro) with transient or permanent ischemia or infarction
- Endoleak
- Fever and localized inflammation

- Genitourinary complications and sequelae (e.g., ischemia, fistula, incontinence, hematuria, impotence, infection)
- Hepatic failure
- Infection of the aneurysm, device access site, including abscess formation, transient fever and pain.
- Local or systemic neurologic complications and sequelae, transient or permanent (e.g., stroke, transient ischemic attack, paraplegia, paraparesis, paralysis, numbness and/or tingling in legs)
- Lymphatic complications and sequelae (e.g., lymph fistula)
- Thrombosis or occlusion of stent graft or arterial vessel of the lower extremities
- Pulmonary/respiratory complications and sequelae (e.g., pneumonia, respiratory failure, prolonged intubation, pulmonary embolism)
- Renal complications and sequelae (e.g., artery occlusion, infarction, insufficiency, failure)
- Secondary procedure
- Stent graft: improper component placement; incomplete component deployment; component migration; suture break; occlusion/thrombosis; infection; stent fracture; graft material wear; dilatation; erosion; puncture and perigraft flow
- Surgical conversion to open repair

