8.7.7. Clinical Events Committee Review

Overview

The clinical events committee (CEC) identified in §2 consists of at least three physicians who will serve as independent experts responsible for evaluation and categorization of adverse events reported by the investigators in the trial. Analyses of events described in this protocol will be based on the CEC-determined categorization.

The primary purpose of these individuals is to ensure a consistent, independent review of events and their clinical significance using standardized criteria and definitions. A curriculum vita for each CEC member is maintained by Endologix, and is available for regulatory review. Due to the need for independence, these individuals may not participate in this trial as investigators, and may not hold significant material, financial or other interests which create a potential conflict with respect to this role, including but not limited to significant equity interest in Endologix.

Process

Endologix will provide independently to the CEC the complete case report form event text that details all deaths and the events as reported by the clinical site investigators. This information will be provided without identification of the site name, and will identify patients by identification number and initials only. Non-serious events or events that are reported as clearly unrelated events will not be assessed by the CEC. The CEC will review events and any follow-up data requested from Endologix. This may include copies of such documents as progress notes, operative notes, discharge summaries, death summaries, and autopsy reports.

The CEC will document the event categorization for each event individually. Meeting notes and supporting information, requests for documentation, etc. will be maintained.

Event Definitions

The following event definitions will be applied to the Primary Endpoint Analysis during this study. Where possible, events will be categorized as being related to the AAA procedure or related to the access site closure.

- *Death*: Any death occurring during the study period, regardless of cause.

Death will be further subcategorized as early (within 30 calendar days from the date of the procedure) or late (>30 days). It will also be subcategorized as aneurysm-related or not aneurysm-related.

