Aneurysm-related death is defined as: any death occurring within 30 days from the date of the procedure, regardless of cause, and death due to aneurysm rupture or following any procedure intended to treat the aneurysm.

- *Procedural Technical Failure*: An event occurring procedurally or within 30 days post-procedurally that meets one or more of the following criteria:
 - *Aortic Stent Graft Failure* is defined as a failure of the bifurcated or fenestrated proximal extension stent graft to be delivered and deployed, such that the procedure is not completed, or the device failure results in a serious complication. The presence of a residual Type I or III endoleak that cannot be resolved during the index procedure is also included in this category.
 - *Renal Stent Graft Failure* is defined as a failure of the renal stent graft to be delivered and deployed, such that the procedure is not completed, or the device failure results in a serious complication.

- *Major Adverse Event*: An event occurring during the trial that meets one of the following criteria:
 - *All-Cause Death* (see above).
 - *Bowel Ischemia*: the lack of adequate blood flow to the intestines that requires intensification of medical therapy or surgical/endovascular intervention.
 - *Myocardial Infarction*: the presence of raised cardiac biomarkers in comparison to laboratory reference ranges.
 - *Paraplegia*: Paralysis of the lower extremities inclusive of the lower trunk.
 - *Renal Dysfunction*: a reduction in estimated glomerular filtration rate (eGFR) of >30% from baseline.
 - *Renal Failure*: the need for temporary or permanent dialysis or >0.5mg/dL increase in pre-operative serum creatinine level at two consecutive intervals.
 - *Respiratory Failure*: pneumonia or respiratory failure requiring ventilator support beyond 24 hours post-procedure.
 - *Stroke*: a sudden development of neurological deficit due to vascular lesions of the brain such as hemorrhage, embolism, or thrombosis that persists for >24 hours.
 - *Blood Loss $\geq 1,000$ cc*: Estimated blood loss during the index procedure $\geq 1,000$ cc.

- *Other Definitions*:
 - *Aneurysm Enlargement*: Core Lab reported aneurysm sac diameter increase of >5mm in late follow-up as compared to the initial post-operative measurement.
 - *Aneurysm Rupture*: internal bleeding or leaking of blood from the aneurysm subsequent to the index procedure.

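### The primary MAE count relies on reported events reaching the CEC, so a recorded blood loss of 1,000 cc or more, or a qualifying creatinine rise, can be left out

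*Combined protocol and SAP*

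**What the plan says.** Section 6.1 lists eight MAE components, among them renal failure and procedural blood loss of at least 1,000 cc, and counts them "defined as the composite of the following as determined by the independent Clinical Events Committee (CEC"). Section 8.7.7 repeats the principle: "Analyses of events described in this protocol will be based on the CEC-determined categorization".

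Section 8.7.7 also describes what the CEC works on. It is "responsible for evaluation and categorization of adverse events reported by the investigators in the trial", and the sponsor sends it "the complete case report form event text that details all deaths and the events as reported by the clinical site investigators". One filter applies before review: "Non-serious events or events that are reported as clearly unrelated events will not be assessed by the CEC".

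The definitions in 8.7.7 make one component wholly numeric and one partly so:

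- **Blood loss:** "Estimated blood loss during the index procedure" of 1,000 cc or more.
- **Renal failure:** either dialysis, or a serum creatinine rise above 0.5 mg/dL over the pre-operative level at two consecutive intervals.

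The trial collects both inputs anyway. Section 6.3 lists "Estimated blood loss" among the procedural evaluations. Section 8.4 schedules creatinine at baseline, pre-discharge, 1 month, 6 months and yearly to 5 years.

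**The concern.** Whether a recorded number crosses a threshold can be settled from the database without anyone filing an event. Under sections 6.1 and 8.7.7, however, the number enters the primary endpoint only if an investigator reports an event, grades it serious, does not call it clearly unrelated, and the CEC then categorizes it. A patient can therefore meet the protocol's MAE definition without the CEC ever seeing the case.

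The 1-month MAE rate would then depend partly on how each of up to 15 sites reports and grades such values. The final report could also contradict itself: the procedural table could show patients with blood loss of 1,000 cc or more who are missing from the MAE table. Section 4.1 says the data are meant to support regulatory approvals, so a reader comparing the two tables would ask why they differ.

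**Working it through.** The document gives no target rate, performance goal or sample-size calculation for the MAE endpoint, so there is no plan figure to reproduce. The check follows the data path and then scales the possible effect.

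**Step 1. Which components are affected.** Blood loss depends only on one recorded number. Renal failure does so only through its creatinine limb; a dialysis patient qualifies without it. Myocardial infarction is also defined by laboratory values, but cardiac biomarkers are not among the scheduled labs (section 8.4), so it cannot be derived for every patient. The exposure is mainly blood loss. By 1 month the only scheduled post-procedure creatinine draws are pre-discharge and 1 month, so just one scheduled pair can meet the two-interval rule.

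**Step 2. Where a qualifying value can drop out.**

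| Route | What the text provides | Outcome |
|---|---|---|
| Value recorded, no event filed | No numeric trigger in 8.6.5, 8.6.6, 8.6.7 or 8.7 | CEC receives no event text |
| Event filed as non-serious | 8.7.7 filter | CEC does not assess it |
| Event filed as clearly unrelated | 8.7.7 filter | CEC does not assess it |
| Event filed as serious and not clearly unrelated | 8.7.7 process | CEC can categorize it as an MAE |

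The second route needs no site error. Under section 8.7.1 an event is serious if it is fatal or life-threatening, requires or prolongs hospitalization, causes lasting or significant disability, or is a congenital anomaly. As a hypothetical case, a 1,200 cc loss without transfusion or a longer stay need not meet any of these. It still meets the MAE definition.

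**Step 3. Effect per patient.** With n = 50 (section 5.1), each omitted patient with no other MAE lowers the rate by 1/50 = 2 percentage points. The direction is one-sided, because omission can only remove events.

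**Step 4. Illustration.** The counts are assumed; the intervals are exact Clopper-Pearson 95%.

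| Patients counted | Rate | 95% CI |
|---|---|---|
| 5/50 | 10% | 3.3 to 21.8 |
| 7/50 (2 restored) | 14% | 5.8 to 26.7 |
| 8/50 (3 restored) | 16% | 7.2 to 29.1 |
| 9/50 (4 restored) | 18% | 8.6 to 31.4 |

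**Step 5. How likely at least one omission is.** Let q be the share of patients who qualify only on a numeric value, and m the share of those not filed or filtered out. Both are assumptions. The expected number omitted is 50qm, and the chance of at least one is 1 − (1 − qm)^50.

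| q | m | Expected omitted | Chance of at least one |
|---|---|---|---|
| 4% | 10% | 50 × 0.004 = 0.2 | 18% |
| 10% | 25% | 50 × 0.025 = 1.25 | 72% |
| 20% | 50% | 50 × 0.10 = 5 | 99.5% |

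The spread shows that the size cannot be fixed from the document.

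**The case against.** The best defence is that the protocol does tell sites to report these cases. Section 8.7 requires all adverse events to be recorded, and 8.7.1 defines them broadly. Section 8.6.5 asks for events during the procedure. Sections 8.6.6 and 8.6.7 ask for adverse findings from diagnostic testing, and section 10.4 counts laboratory tests as diagnostic tests, so a creatinine rise is reasonably covered. Sections 6.1 and 8.7.7 tell sites that a 1,000 cc loss is a major adverse event. Section 10.1(g) describes the CEC's remit more widely, taking in CRFs and source documents, and 8.7.7 lets it obtain operative notes. Monitors also check CRFs against hospital records.

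Much of this stands. It makes non-filing less likely, above all for creatinine. But none of these provisions sets a numeric trigger or compares recorded values with the MAE definitions, and the wider remit in 10.1(g) still concerns what investigators documented as events or complications. Nor does any of them remove the seriousness and relatedness filter, which acts on events that were properly filed.

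A reader might go further and infer that sites have no reason to file blood loss alone, because the anticipated-event list in 8.7.4 names "Bleeding requiring transfusion and/or surgical intervention". That does not follow. The same list includes bleeding as an example of arterial damage, with no transfusion condition, and includes renal insufficiency and failure. It is a list of possible events, not a reporting rule.

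**Conclusion.** The gap is real and worth closing. As written, the path to the primary safety endpoint lets a patient who meets a numeric MAE definition go uncounted, even at a site that follows the protocol. The exposure is chiefly blood loss; creatinine is a lesser case.

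Each affected patient without another MAE costs 2 points at n = 50, always downward. How many there would be is unknown, and the counts and shares above are assumptions.

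The document does not support saying that such values will not be counted, or that the reported rate is biased. No sentence states it, and compliant sites may file most of these cases as serious. The SAP and CRFs (Attachments 5 and 3) are listed without their text, so a derivation rule may exist there. If it does, it still has to be reconciled with the CEC-only wording of sections 6.1 and 8.7.7.

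**What to change.** State in sections 6.1 and 8.7.7 and in the SAP that:

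1. Procedural blood loss of at least 1,000 cc and the creatinine criterion of Renal Failure are derived for every patient from the recorded estimated blood loss and serum creatinine. A patient over the threshold counts as having an MAE whether or not an event was filed.
2. Every threshold crossing is listed for the CEC regardless of filing, reported seriousness or relatedness. The CEC may confirm the data, but the count does not wait for a site report.
3. The derived list is reconciled with the CEC list before analysis, and differences are documented.

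Two definitions are needed for the derivation to run. Say which creatinine measurements form two consecutive intervals by 1 month, including whether unscheduled draws count and how a 1-month draw late in the 30 ± 14 day window (up to day 44) is treated. Say also how the criterion applies to patients on dialysis at baseline, for whom section 5.3 waives the creatinine exclusion.

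If the SAP or CRFs already contain such a rule, only the wording of 6.1 and 8.7.7 needs to be aligned with it.

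The cost is a few sentences, one data listing and one reconciliation step. No new data are collected. The downside for the sponsor is a possibly higher reported MAE rate.

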6.2. FEASIBILITY/EFFECTIVENESS

Feasibility/effectiveness is defined as successful device delivery and deployment with patency of the renal and aortic endografts without Type I/III endoleak as determined by the Core Lab at 1 month.

Specific definitions applicable to this endpoint are as follows:

- *Procedural Feasibility:*
 - Successful bifurcated and fenestrated/scalloped proximal extension stent graft delivery and deployment without residual Type I or Type III endoleak; and,
 - Successful renal stent graft delivery and deployment with target vessel patency.
- *Clinical Feasibility:*
 - Maintenance of bifurcated and fenestrated/scalloped proximal extension stent graft patency, without Type I or Type III endoleak at each follow-up; and,
 - Maintenance of target visceral vessel patency at each follow-up.
- *Assisted Clinical Feasibility:*
 - Maintenance of bifurcated and fenestrated/scalloped proximal extension stent graft patency, without Type I or Type III endoleak aided with a secondary procedure; and,
 - Target visceral vessel patency at each follow-up aided with a secondary procedure.

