- Secondary procedures within 30 days, at six months, and at years 1 through 5 for resolution of endoleak, limb occlusion, migration, aneurysm sac expansion and/or a device defect.

Schedule of Tests:

Pre-procedural high resolution, contrast-enhanced CT scan evaluation to determine anatomical eligibility for enrollment will be performed within three months of the procedure. A physical exam and laboratory testing will be performed prior to the procedure. Following EC/IRB approval and patient written informed consent, the patient will be screened for eligibility. Patients will be followed procedurally and to hospital discharge, and will then be followed at intervals: 1 month; 6 months; 1 year; and annually to 5 years. Tests and evaluations:

Schedule of Tests:	Screening/ Baseline	Procedure (Day 0)	Pre- Discharge	1 Month*	6 Months*	1 to 5 Years*
Physical Exam [†]	x		x	x	x	x
Blood Labs [‡]	x		x	x	x	x
Contrast-Enhanced CT scan [§]	x			x	x	x
Ankle Brachial Index	x		x	x	x	x
Adverse Events		x	x	x	x	x

[†]The physical exam includes overall health and physical assessment and vital signs.

[‡]Blood labs include serum creatinine, blood urea nitrogen, hematocrit, and hemoglobin.

[§]The baseline high resolution, contrast-enhanced CT scan (3mm or less slice spacing) performed within three months prior to enrollment will be reviewed by the independent core lab for patient eligibility determination. Evaluations of endograft performance, renal stent graft patency and integrity, and stent graft patency and integrity will be made based upon post-operative CT scan evaluations by the core laboratory.

*Follow-up windows are ±2 weeks (1 month visit); ±1 month (6 month visit); ±2 months (Year 1 visit); ±3 months (Years 2 through 5 visits)

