- **Stent Graft (Fenestrated/Bifurcated) Patency and Integrity** within 30 days, at six months, and annually at 1 through 5 years, as determined by contrast-enhanced CT scan and as assessed by the independent core laboratory, inclusive of:
 - Patent luminal flow
 - Absence of kinking or occlusion
 - Absence of stent fracture
 - Absence of graft fatigue or failure
- **Secondary Procedures** within 30 days, at six months, and annually at 1 through 5 years for resolution of endoleak, limb occlusion, migration, aneurysm sac expansion and/or a device defect.

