7. STUDY MATERIALS

7.1. DEVICE DESCRIPTION

The commercially-available endovascular system consists of two primary components: an implantable bifurcated stent graft and a disposable delivery catheter. The pre-loaded stent graft is inserted endoluminally via the femoral artery over a .035” guidewire and upon deployment and withdrawal of the delivery system, expands to the indicated diameter.

Bifurcated stent grafts (**Figure 1**) are composed of a CoCr alloy wire stent cage[†] with a thin-walled, high density expanded polytetrafluoroethylene (ePTFE) graft cover that is attached proximally and distally to the stent cage with polypropylene suture. Bifurcated devices have body lengths ranging from 60 to 100mm. Limb dimensions include lengths ranging from 30mm to 55mm and diameters of 13 or 16mm to accommodate various patient anatomies. Devices are delivered through a 21Fr catheter system having an integrated introducer sheath. Accessory limb extensions in straight, stepped, flared, and tapered configurations are available.

[†]The incoming wire is certified to meet ASTM F1058:2002, *Standard Specification for Wrought 40Cobalt-20Chromium-16Iron-15Nickel-7Molybdenum Alloy Wire and Strip for Surgical Implant Applications (UNS R30003 and UNS R30008)*.

[figure not shown]
Figure 1. Bifurcated Stent Graft

The investigational fenestrated proximal extension stent graft system consists of two primary components: an implantable fenestrated/scalloped stent graft and a disposable delivery catheter system. The pre-loaded stent graft is inserted endoluminally via the femoral artery over a .035” guidewire and upon deployment and withdrawal of the delivery system, expands to the indicated diameter.

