8.7.3. Reporting of SAEs

Any SAE occurring during the study period must be recorded on the appropriate **ADVERSE EVENT** CRF and **Serious Adverse Events** section of the CRF.

For any SAE, fax the ADVERSE EVENT CRF within 24 hours of awareness to the Endologix Clinical department at [contact]. All patients with an SAE must be followed and outcomes reported. The Investigator should supply to Endologix and the responsible EC/IRB with a complete, written case history (AE forms) and any additional requested information (e.g., other diagnostic testing, discharge reports, autopsy reports, etc.).

Deaths

For any patient death, regardless of cause or timing, an autopsy should be requested. If the family has agreed to the conduct of an autopsy, the autopsy report is to be attached to the **ADVERSE EVENT** CRF where the death is reported.

A device explant kit will be provided to the hospital for processing and shipment to an independent pathologist per established methods. To request a kit, send a fax to Endologix at [contact], or contact Endologix by telephone at [contact].

In all cases, the death certificate is to be attached to the **ADVERSE EVENT** CRF where the

death is reported. Every attempt should be made to obtain as much detailed information on the events or conditions leading up to the death as possible. If the patient was hospitalized, a copy of the discharge summary source document is required.

Secondary Interventions

For patients that experience any non-diagnostic invasive secondary treatment of the groin access areas or of the abdominal aortoiliac vessels (e.g., hematoma drainage, vascular exploration for bleeding, iliac stenting, thrombectomy, additional device placement for endoleak, embolization for Type II endoleak, etc.), it is important to identify the area, region or vessel segment that is involved and the specific procedure performed on the relevant **ADVERSE EVENT CRF**. A copy of the discharge summary source document is required.

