- *Conversion to Open Repair*: open surgical repair of the abdominal aortic aneurysm due to unsuccessful delivery or deployment of the stent graft, due to complications or other clinical situations that precluded successful endovascular treatment, or at any time following initial successful endovascular treatment for any reason.
- *Cardiac Morbidity*: acute myocardial infarction (diagnosed based on measured levels of one or more cardiac biomarkers in comparison to laboratory reference ranges); new onset heart failure (an acute episode or exacerbation of existing low cardiac output accompanied by distal and/or pulmonary edema); intractable or malignant arrhythmia requiring cardioversion or pacemaker placement; or coronary intervention (coronary artery bypass grafting [CABG] or percutaneous coronary intervention [PCI]).
- *Clinically Significant Device Migration*: Core Lab reported aortic stent graft movement >10mm from the original implant location resulting in an intervention or in a serious complication.
- *Renal Dysfunction*: a reduction in the estimated glomerular filtration rate (eGFR) of >30% from the preoperative value.
- *Secondary Procedure*: any non-diagnostic intervention after the index procedure intended to correct or repair an endoleak, limb occlusion, migration, aneurysm sac expansion and/or a device defect.
- *Stent Graft Occlusion*: intervention for aortic or renal stent graft occlusion or as reported by the Core Laboratory at any time in follow-up.
- *Transient Ischemic Attack*: a sudden development of neurological deficit due to vascular lesions of the brain such as hemorrhage, embolism, or thrombosis that persists for <24 hours.
- *Type I/III/IV Endoleak*: Core Lab reported endoleak: between the endograft and the vessel either at the proximal attachment point (Type IA), or at the distal attachment point (Type IB), or between endograft components (Type III) or transgraft (Type IV).
- *Type II Endoleak*: Core Lab reported endoleak emanating from a patent collateral vessel (e.g., inferior mesenteric artery, lumbar artery).

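### The Secondary Procedure definition omits re-treatment of renal stenosis or occlusion, although Assisted Clinical Feasibility relies on it

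*Combined protocol and SAP*

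**What the plan says.** Section 6.2 of the protocol defines three feasibility measures. Assisted Clinical Feasibility has an aortic part and a visceral part. The visceral part is "Target visceral vessel patency at each follow-up aided with a secondary procedure".

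Section 8.7.7, under Other Definitions, says what a Secondary Procedure is: a non-diagnostic intervention after the index procedure that is "intended to correct or repair an endoleak, limb occlusion, migration, aneurysm sac expansion and/or a device defect". Section 6.3 lists Secondary Procedures as an additional evaluation, counted when performed "for resolution of endoleak, limb occlusion, migration, aneurysm sac expansion and/or a device defect". The Synopsis repeats the item: "Secondary procedures within 30 days, at six months, and at years 1 through 5 for resolution of endoleak, limb occlusion, migration", followed by the same remaining purposes.

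Section 8.7.7 has a separate term, Stent Graft Occlusion, which covers an intervention for occlusion of an aortic or renal stent graft, or an occlusion reported by the Core Lab. It is not linked to Secondary Procedure.

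**The concern.** The term that decides Assisted status for a visceral vessel is defined elsewhere by a list with no visceral item. The renal stent graft is one of the study devices named in the Synopsis. Section 6.3 has the Core Lab assess it for stenosis and occlusion, and section 8.7.4 lists renal artery occlusion among the anticipated events. The protocol therefore foresees the event that its list of secondary procedures leaves out.

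Two reported rates are at stake. The Secondary Procedures rate would not count a re-intervention that restores the patency of an investigational component. The Assisted Clinical Feasibility rate could come out differently for two analysts, one following section 6.2 and the other section 8.7.7.

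**Working it through.** The documents give no figure to reproduce. The check compares definitions and then works out what one patient does to each rate.

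**Step 1: is the list closed?** Section 8.7.7 names five purposes: endoleak, limb occlusion, migration, sac expansion and device defect. It has no wording that marks them as examples. Section 6.3 and the Synopsis give the same five.

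**Step 2: can a renal re-opening fit one of the five?**

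- *Limb occlusion.* Section 7.1 uses limb for the bifurcated graft ("Limb dimensions include lengths ranging from 30mm to 55mm"), and section 8.7.7 gives renal stent graft occlusion a term of its own. Limb occlusion does not naturally include it.
- *Device defect.* A fractured or torn renal stent graft could be placed here. A narrowed or thrombosed graft without a defect does not readily fit.
- *Endoleak.* A Type III endoleak at a fenestration would fit. Stenosis or occlusion without an endoleak would not.
- *Migration and sac expansion.* Neither describes loss of renal patency.

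What remains outside is re-treatment for renal stenosis or occlusion with no device defect and no endoleak.

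**Step 3: does the definition govern?** Section 8.7.7 introduces its list with "The following event definitions will be applied to the Primary Endpoint Analysis during this study". A footnote in section 6.3 also sends the reader to section 8.7.7 for event definitions. The link is direct for the Secondary Procedures evaluation. For section 6.2 it rests on the general sentence just quoted and on the use of the same term.

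**Step 4: what is recorded in any case?** Section 8.7 requires all adverse events to be recorded. Intervention for renal stent graft occlusion has its own label. Intervention for renal stenosis short of occlusion has none. The data exist, and the fault is in how they are classified.

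**Step 5: size.** N = 50 is the maximum enrollment in the Synopsis and section 5.1. Let k be the number of patients whose only re-intervention is for renal stenosis or occlusion and who are then patent without Type I/III endoleak. The documents do not give k.

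- Shift in the affected rate = 100 × k/N percentage points.
- For one patient: 100 × 1/50 = 2.0 points.
- For k = 0, 1, 2, 3, 4, 5: 0, 2, 4, 6, 8, 10 points.

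Illustration with assumed counts: 50 patients treated and evaluated, 46 unassisted successes, k = 2 and 2 failures. No other patient has a secondary procedure. The Assisted rate is taken as cumulative, meaning unassisted plus assisted successes. Intervals are exact (Clopper-Pearson) 95%.

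| Rate | Renal re-treatment counted | Five-purpose list applied |
|---|---|---|
| Secondary Procedures | 2/50 = 4.0% (0.5 to 13.7) | 0/50 = 0% (0 to 7.1) |
| Assisted Clinical Feasibility | 48/50 = 96.0% (86.3 to 99.5) | 46/50 = 92.0% (80.8 to 97.8) |

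Both differences are 100 × 2/50 = 4.0 points.

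**The case against.** The strongest reply is that section 6.2 is the specific rule. It grants Assisted status for visceral patency in so many words, and the Synopsis sends the reader to section 6.2 for the feasibility definitions. Unlike section 6.1, section 6.2 does not point to section 8.7.7. To let the list cancel the visceral part would leave that part almost nothing to do, so an analyst would most naturally follow section 6.2. This stands against a stronger reading that a reader might infer, namely that a renal re-opening cannot earn Assisted status. The documents show a conflict, not a prohibition. The reply does not help the Secondary Procedures rate, where sections 6.3 and 8.7.7 and the Synopsis all use the list.

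A second reply is that some renal re-interventions do fall within the list and that renal occlusion is visible elsewhere, both under its own term and in the Core Lab assessment in section 6.3. That is also right. It would be wrong to say that every renal re-intervention is left out or that the signal is hidden.

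A reader might also cite the CRF instruction in section 8.7.3, which asks for detail on "any non-diagnostic invasive secondary treatment of the groin access areas or of the abdominal aortoiliac vessels". It is weak support. It uses a different term, its examples are open-ended, and it does not define an endpoint.

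Finally, the Statistical Analysis Plan is listed as Attachment 5, but its text was not available for this check and may define the term. That would help the analyst, but the protocol sections would still disagree.

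**Conclusion.** The point holds in a narrow form, and it is minor. The protocol's definition of Secondary Procedure excludes re-treatment of a renal stent graft or target renal artery for stenosis or occlusion without a device defect or endoleak, while the visceral part of Assisted Clinical Feasibility presupposes that such re-treatment is included. The Secondary Procedures rate omits these patients as written. The Assisted rate depends on the section followed.

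The size is 2.0 percentage points per such patient at N = 50. The total is unknown because the documents give no count, and the counts in the table above are assumptions.

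A reader might go further and infer a bias in the 1-month feasibility result. The documents do not support this. That result is defined by status at the visit, "patency of the renal and aortic endografts without Type I/III endoleak as determined by the Core Lab at 1 month". Its wording reads as counting a patient who was re-treated earlier and is patent on that CT, and it does not use the disputed term. The visible text contains no performance goal, so no decision is shown to change.

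**What to change.** Add re-intervention for stenosis or occlusion of a renal stent graft or target visceral vessel to the Secondary Procedure definition in section 8.7.7. Make the same addition to the lists in section 6.3 and the Synopsis. The Secondary Procedures and Assisted Clinical Feasibility rates then use one definition. Issue it as a dated clarification before the rates are tabulated.

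The cost is a one-line change in three places. It needs no new visit or test, because the events are already recorded. The drawback is that the reported Secondary Procedures rate may become slightly less favorable, since a wider definition can add patients but cannot remove any.
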